
etc.) to show appreciation. STRIDE sites will be unaware that they will receive a thank-you gift bag and therefore would not be considered as an incentive for study participation.

Patient sample. Clinical criteria for STRIDE participation at each site will include: Age >= 60, admission for medical illness, community-dwelling (i.e. not in a nursing home), not requiring inpatient physical therapy, ability to follow one-step commands and to ambulate safely and independently.

Outcomes. Implementation outcomes. Penetration (primary outcome) is defined as the proportion of eligible hospitalizations with at least one documented STRIDE walk. It is not possible to assess all eligibility criteria in the EHR (e.g. able to walk at baseline); thus, with this more inclusive denominator, 100% penetration is not an appropriate goal. Based on preliminary data, we anticipate penetration to range from 0% (no program activity at 10-month outcome assessment) to 40% (estimated maximum achievable based on data from current STRIDE sites). Fidelity will be assessed for eligible hospitalizations with at least one documented STRIDE walk as the percentage of eligible hospital days with "full dose" of the program, defined as two or more documented walks or one for more than five minutes. Program adoption is defined as ≥ 5 general medicine patients with a STRIDE walk in the EHR within month 5 or 6 from start date with Function QUERI. We will assess implementation outcomes at 10 months (primary), as all current STRIDE sites have launched within this time frame, and also at 13, and 16 months to describe trajectories and assess sustainment, given that we have observed the dynamic nature of STRIDE program activity at some sites.

Effectiveness Outcomes/Quality metrics: Consistent with previous literature on the impact of hospital walking programs we will focus on hospital **length of stay** (LOS) due to its importance to patients and implications for overall facility efficiency and performance reporting (e.g., SAIL measures). Other important effectiveness outcomes will include inpatient fall rates (assessed using Inpatient Evaluation Center or IPEC), and discharge to nursing home (defined using established procedures combining VA + Medicare data sources).

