Analyses. To address the question: How should the STRIDE clinical program be adapted to optimize sustainability? We will use the FRAME to classify STRIDE adaptations at 17 VAMCs that have started programs (via VISN 6 rollout, ongoing Function QUERI trial or other means). Data sources will include study team notes, communications, interview transcripts, and data collected on Diffusion Network calls. Responses will be coded and analyzed at site levels to develop facility-level summaries of STRIDE adaptations, indicating where there is divergence in responses at the site-level. From this coded data, we will identify and visually display emergent themes in a matrix, with columns reflecting implementation outcomes (i.e., fidelity and penetration) arranged from high to low, to illustrate patterns in program adaptations according to implementation outcomes. To address the question: Are there differences in implementation outcomes (penetration, fidelity) at 10 months (primary), 13, 16 months between arms? We hypothesize that sites randomized to enREP will have higher penetration (proportion of eligible patients with ≥ 1 STRIDE documented walk during hospitalization) and fidelity (eligible hospitalizations with at least one documented STRIDE walk as the percentage of eligible hospital days with "full dose" of the program, defined as two or more documented walks or one for more than five minutes.). We will use generalized linear models⁷⁵ to examine the effect of foundational vs. enREP on implementation outcomes at 10-months. The main predictors of interest will be foundational REP vs. enREP and stratification variables used in the covariate constrained randomization (described above). We will examine how fidelity and penetration outcomes change over time using descriptive methods (e.g. plots, descriptive statistics, subgroups). To address the question: What is the impact on effectiveness outcomes and quality metrics (hospital length of stay or discharge to nursing home) at implementing sites? In exploratory analyses, we are interested in assessing the impact of STRIDE on hospital LOS, discharge to nursing home, and inpatient fall rates. Our sample of Veterans for this analysis will

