come from sites that adopt STRIDE (approximately 95,000 Veterans). The sample of Veterans will be from those who are hospitalized and meet our patient eligibility criteria; some of those patients will have participated in STRIDE (i.e. treatment group) and some will have not (i.e. comparison group). Data sources include CDW, VA/CMS repository data, GEC Health Care Risk measures and Geriatrics and Extended Care Data Analysis Center (GECDAC) Residential History File data. We will use inverse-probability of treatment weighted methods to adjust for confounding and estimate an average causal treatment effect for STRIDE. The study team will determine a priori which covariates are likely to be key determinants of receiving STRIDE. Qualitative data collection and approaches to data integration have been described previously.

Sample size estimate. Sample size calculations were conducted for the implementation outcomes at 10-months. Using a two-sided t-test based on a sample size of a minimum of 32 sites (at least 16 foundational REP and at least 16 enREP), a type-1 error rate of 5%, we will have 80% power to detect an effect size difference of 1.0 and 90% power to detect an effect size difference of 1.2 between arms. For the primary penetration implementation outcome, assuming a standard deviation of approximately 9% based on preliminary data from ongoing work, these effect size differences correspond to a mean difference of 9% between arms for 80% power and 10.8% for 90% power, with enREP having the higher penetrance.

Leadership. [name], a geriatrician, is the Corresponding PI for the Function QUERI program. [name] leads Durham's COIN ADAPT, and has substantial clinical, research and leadership expertise relevant to implementing and evaluating new clinical programs in VA.

Implementation Project 3: Caregivers FIRST

Urgency of expanding supports to family caregivers and relationship to ICF. 2 million Veterans with functional and/or cognitive impairment in VA receive informal care, e.g., care from a family member or friend, and this support is a key determinant of whether or not function and independence are preserved. These caregivers are currently

Objective	Improve caregiver and Veteran functioning through caregiver skill training and support
Evidence	Van [name] et al. Family caregiver skills training to improve experiences of care: a randomized clinical trial. J Gen Intern Med 2019 Oct;34(10):2114-2122.
Primary Partners	VA Caregiver Support Program

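### The exploratory STRIDE effectiveness analysis defines neither participation nor time zero, so its length-of-stay contrast is open to immortal-time bias that admission-based weights would not remove

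*Combined protocol and SAP*

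**What the plan says.** Under Implementation Project 2: STRIDE, Analyses, the plan states: "In exploratory analyses, we are interested in assessing the impact of STRIDE on hospital LOS, discharge to nursing home, and inpatient fall rates". The sample is about 95,000 eligible Veterans hospitalized at adopting sites, of whom "some of those patients will have participated in STRIDE (i.e. treatment group) and some will have not (i.e. comparison group". The method is given in one sentence: "We will use inverse-probability of treatment weighted methods to adjust for confounding and estimate an average causal treatment effect for STRIDE". Covariates are left open: "The study team will determine a priori which covariates are likely to be key determinants of receiving STRIDE". "Data sources include CDW, VA/CMS repository data, GEC Health Care Risk measures" are named, with residential history data. The STRIDE text under Data Analysis and Statistical Considerations repeats the comparison and adds no definition or time origin.

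Receipt is made operational only for the implementation outcomes. Outcomes defines penetration as "the proportion of eligible hospitalizations with at least one documented STRIDE walk", and the hypothesis restates it as the "proportion of eligible patients with ≥ 1 STRIDE documented walk during hospitalization". Neither sets a deadline within the stay. "Fidelity will be assessed for eligible hospitalizations with at least one documented STRIDE walk as the percentage of eligible hospital days" at full dose, so fidelity grades days among patients who have already walked. The fidelity hypothesis under Data Analysis and Statistical Considerations is worded differently: it speaks of the share of participants who have a supervised walk, which implies that a participant could have none.

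Outcomes also concedes that some eligibility criteria, with ability to walk at baseline as the example, cannot be assessed in the EHR.

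**The concern.** A patient must still be in hospital on the day of the first walk to be counted as having walked. If any walk during the stay defines treatment, group membership depends on LOS, which is the lead effectiveness outcome. Patients discharged before a walk could happen fall into the comparison group, and treated patients' days before the first walk are credited to STRIDE. Taken alone, this makes STRIDE look as if it lengthens stays, or hides a real shortening. Propensity weights built from admission covariates balance those covariates; they do not undo a classification that depends on later survival in hospital.

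At stake is an estimate with a causal label, on an outcome chosen for its importance to patients and for facility performance reporting, from a sample large enough to make a modest artefact look precise. Omitting the time origin is not a convention of this protocol: the parallel Caregivers FIRST analysis starts its six-month home-time window at the consult.

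**Working it through.** The plan gives no effect size or power for this analysis, and the 95,000 is stated without derivation, so there is no figure to reproduce. The check asks what an ever-walked versus never-walked contrast shows when STRIDE has no effect.

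**Inputs.** Penetration 10%, 20% and 40%; Outcomes anticipates 0% to 40%, with 40% the estimated maximum. Mean LOS M = 4.7 days is an assumption: the documents give it only as a stratification cut. LOS shape is also assumed: geometric, or lognormal with CV 0.6 to 1.0 (SD 2.5 to 4.2 overall). Delivery: a subset of patients is served and, in that subset, the first walk occurs with daily chance h from day s. This fits the Background description of an assessment followed by daily walks.

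**Identity.** With penetration π and mean LOS E1 (walked) and E0 (never walked), M = πE1 + (1 − π)E0. Hence E1 − E0 = (E1 − M)/(1 − π).

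**Geometric LOS, by hand.** Let t = (1 − h)(1 − 1/M), where 1 − 1/4.7 = 0.787. Then E1 = M + (s − 1) + t/(1 − t). Example, h = 0.5 and s = 2: t = 0.394, t/(1 − t) = 0.649, E1 = 4.7 + 1 + 0.649 = 6.349. At π = 0.40 the artefact is 1.649/0.60 = +2.75 days; at π = 0.10 it is 1.649/0.90 = +1.83.

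| Walks from | Daily chance | E1, geometric | Artefact at 10% / 40%, geometric | Range over all shapes, 10–40% |
|---|---|---|---|---|
| day 1 | 80% | 4.887 | +0.21 / +0.31 | +0.03 to +0.31 |
| day 1 | 50% | 5.349 | +0.72 / +1.08 | +0.19 to +1.09 |
| day 2 | 80% | 5.887 | +1.32 / +1.98 | +0.14 to +1.97 |
| day 2 | 50% | 6.349 | +1.83 / +2.75 | +0.44 to +2.75 |

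The last column is simulated (500,000 stays per shape), so it differs from the hand figures by simulation noise. The upper ends come from geometric LOS at 40% penetration. With lognormal shapes alone, the upper ends in the last three rows fall to about +0.73, +0.97 and +1.72. If every first walk falls on the admission day, E1 = M and the artefact is zero.

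**Does weighting remove it?** A measured binary severity was added: 40% prevalence, mean LOS 6.5 versus 3.5 days (0.4 × 6.5 + 0.6 × 3.5 = 4.7), halving the chance of walking. Correct inverse-probability weights still left +0.04 to +2.01 days (80% daily chance) and +0.18 to +2.73 (50%), across both start days and penetration of 10% and 40%.

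**Does alignment remove it?** In the same setting a weighted landmark gave −0.02 to +0.07 day. Patient-day exposure switching on after the first walk gave a discharge risk ratio of 0.990 to 1.006. Severity was fixed at admission, so confounding that changes during the stay was not tested.

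**Nursing-home discharge.** Assuming a rate near 5% with log-odds rising 0.05 to 0.10 per day of stay, the weighted ever/never contrast was off by +0.01 to +1.5 percentage points in the served subset; the landmark stayed within 0.1 point of zero.

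**Precision.** The 95% half-width is 1.96 × SD × √(1/n1 + 1/n0). SD 2.5 with 38,000 and 57,000 gives 0.03 day; SD 4.2 with 9,500 and 85,500 gives 0.09 day. An assumed design effect of 4 for site clustering doubles these to 0.07 and 0.18.

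**The case against.** The walk definition belongs to penetration, not to this analysis. The fidelity wording under Data Analysis and Statistical Considerations, and the assessment that opens the program, leave room for another meaning of participant. The weighting sentence does not exclude time-varying weights, and covariate choice is deferred to an a priori decision. The analysis is exploratory. With prompt day-1 walks at low penetration, the artefact is a few hundredths to about two tenths of a day.

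All of that stands, and it rules out a stronger reading: a reader might infer that the plan commits to an ever/never comparison with weights fixed at admission. It does not; it leaves the matter unspecified. The objection does not remove the need for a definition, since participation starting at a post-admission assessment would still leave time in hospital before exposure.

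A second objection is that a landmark is not clearly better, because patients who could never walk would remain in the comparison group and could tilt the result towards STRIDE. This is fair. The criterion excluding patients who need inpatient physical therapy may screen out some of them, if it can be ascertained, but the documents give no share or LOS for this group. The opposing bias therefore cannot be sized. Two biases that may partly cancel are not a reason to keep either.

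**Conclusion.** The omission is certain: both places that describe the analysis lack a definition of participation, a time zero and any time alignment. The bias is conditional on any walk during the stay defining treatment. Its size depends on when first walks occur, which the documents do not report. Under the stated assumptions it runs from nothing, through a few tenths of a day at most with prompt day-1 walks, to upper ends of about +1 to +2.7 days when walks are slower or start on day 2.

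Two further inferences are not supported. One is a bias of several days: giving every patient the same low daily chance of a first walk yields +1.4 to +4.7, but that fits the described delivery poorly. The other is that the published estimate must run against STRIDE: immortal time alone does, but unmeasured walking ability may push the other way, so the net sign is open. The randomized comparison of implementation strategies is untouched. The causal label and the narrow intervals make this worth fixing even in an exploratory analysis.

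**What to change.** Reconcile the wordings of participation and define exposure by the date of the first documented walk, with admission as time zero. Replace any ever/never contrast with a time-aligned one. Preferably, use patient-day records in which exposure switches on at the first walk. Alternatively, use an early landmark, chosen from first-walk timing before LOS is examined, with weights on covariates known by then and remaining LOS as the outcome. Apply the same alignment to nursing-home discharge and, where fall records can be linked to patients, to falls. Use time-updated weights only if covariates by hospital day are available; none are listed.

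State how baseline function will be handled: restrict or adjust with EHR proxies, such as the GEC risk measures if they capture it. Otherwise report associations and drop the causal label.

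The cost is SAP wording and programming; walks, hospital days, and admission and discharge dates are already used or collected. A landmark has further costs. It changes the estimand and drops short stays (about 1–21% after day 1 and 14–38% after day 2 under the assumed shapes). It also counts later walkers as unexposed (4–46% of eventual walkers still in hospital in the served-subset settings), which would dilute a real effect. If walks begin on day 2, a landmark after day 1 has no exposed patients.

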community (home time) over a 6-month period. Our sample of Veterans for this analysis will come from sites that adopt Caregivers FIRST nationally (that is, not limited to the 25 enrolled sites). The sample of Veterans (approximately 20,000) will be from those whose caregiver received consults for VA caregiver education and training services, including to Caregivers FIRST over a year period after the program was announced as a minimum standard; some of those caregivers will attend Caregivers FIRST classes (i.e., treatment group) and some will not (i.e., comparison group). Data sources include CDW, VA/CMS repository data, Caregiver Support Program Data, and Geriatrics and Extended Care Data Analysis Center (GECDAC) Residential History File data. We will use inverse-probability of treatment weighted methods to adjust for confounding and estimate an average causal treatment effect for Caregivers FIRST on home time over the 6-month time period following the consult for a VA caregiver education and training. We use the same modeling approach described above to examine the effect of implementation approach on general program quality scores and size of the general caregiver program. In exploratory analysis, we are interested in assessing the impact of Caregivers FIRST on Veteran's days in the community over a 6-month period. Our sample of Veterans for this analysis will come from sites that adopt Caregivers FIRST. The sample of Veterans will be from those whose caregiver received consults for VA caregiver education and training services, including to Caregivers FIRST over a year period; some of those caregivers will attend Caregivers FIRST classes (i.e. treatment group) and some will not (i.e. comparison group). We will use inverse-probability of treatment weighted methods to adjust for confounding and estimate an average causal treatment effect for Caregivers FIRST on home time over the 6month time period following the consult for a VA caregiver education and training. The study team will determine a priori which covariates are likely to be key determinants of attending Caregivers FIRST training. We will explore the distribution that best fits the days at home outcome: Poisson, Negative Binomial, or zero-inflated. Generalized linear models with inverse propensity score weights will be used. We will describe the quality metrics using descriptive statistics, but these will not be modeled. Qualitative data collection and approaches to data integration have been described previously. To address the key questions: What are the costs for delivering one round of Caregivers FIRST training? What are the costs of the high- and lowintensity implementation support? The business case will include a budget impact analysis to help VA administrators consider the cost of implementation and delivery along with the effectiveness of the intervention in the context of the VA priorities to improve Veteran outcomes. The budget impact analysis will evaluate implementation costs for each strategy and intervention delivery costs per participant. The high-touch implementation support strategy is expected to use more resources (delivery time and attendance time) and potentially improve implementation outcomes, for example improved fidelity or increased penetration. To assess the value of the additional investment in implementation support, we will describe implementation costs per enrolled participant for each implementation strategy. While the overall resource use might be higher, a lower cost per participant would indicate a high value. We will use staff time and equipment data from the adaptations survey (baseline, 6 months, and 12 months) to assess costs using U.S. Veterans Health Administration salary and managerial cost accounting data. Drawing from methods in prior Function QUERI work, Business Case Analysis (BCA) will frame affordability to VA. For the cumulative 12-month study period, two types of costs will be collected for each site using a standardized method to track implementation activities 1) clinical delivery team costs incurred and 2) implementation strategy costs incurred. Because the 25 sites enrolled will represent a fraction of the sites nationally who will also implement (expect over 100 to implement), we can extrapolate to a national scenario in the BCA.

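### The exploratory weighted patient-level analyses of STRIDE and Caregivers FIRST provide for site neither in the weights nor in the variance

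*Combined protocol and SAP*

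**What the plan says.** **STRIDE** (Implementation Project 2, Analyses; repeated under Data Analysis and Statistical Considerations). Among eligible hospitalized Veterans at adopting sites, about 95,000 in all, those who took part in STRIDE are compared with those who did not. The method is given in one sentence: "We will use inverse-probability of treatment weighted methods to adjust for confounding and estimate an average causal treatment effect for STRIDE". On covariates the plan adds: "The study team will determine a priori which covariates are likely to be key determinants of receiving STRIDE". None is listed. The status is clear: "In exploratory analyses, we are interested in assessing the impact of STRIDE on hospital LOS", together with nursing home discharge and inpatient falls.

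**Caregivers FIRST** (Implementation Project 3, Analyses; repeated in the same later section). The outcome is Veteran days at home over six months, at adopting sites nationally. "The sample of Veterans (approximately 20,000) will be from those whose caregiver received consults for VA caregiver education and training services". Attenders are compared with non-attenders, and the model is named: "Generalized linear models with inverse propensity score weights will be used". The covariate rule is the same: "The study team will determine a priori which covariates are likely to be key determinants of attending" the training. Specific Aim 2, to which this analysis belongs, is labelled exploratory.

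For these two analyses no section mentions a site term, a random effect, GEE, weighting within site, or a variance clustered on site.

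**The concern.** Veterans at one hospital share admission practice, discharge options and staffing, so their outcomes are correlated. If whether a Veteran takes part also depends on the site, ignoring site has two separate consequences. The standard error of the treated-versus-untreated contrast is too small. And if high-uptake sites tend to have systematically shorter or longer stays, that difference is read as a program effect.

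For STRIDE the plan itself gives reason to expect both ingredients. Penetration is anticipated to run from 0% to 40% across sites, with a standard deviation of about 9%. Site-level adjusted length of stay (cut at 4.7 days) is a randomization stratifier, chosen among characteristics thought likely to bear on implementation outcomes, and penetration is one of those. The randomized comparison is adjusted for the stratifiers. The non-randomized comparison, which needs adjustment more, carries no such commitment.

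The plan calls its target an average causal treatment effect, and the Caregivers FIRST business case is meant to set cost beside effectiveness. An interval that looks very precise because it rests on tens of thousands of Veterans could carry weight despite the exploratory label.

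**Working it through.** **What can be reproduced.** The counts of 95,000 and 20,000 come with no formula, precision, ICC or design effect, so there is nothing to reproduce for these analyses. The plan's power figures belong to the randomized site comparison. They reproduce to within 2 points (STRIDE, 16 v 16: 78.1% at effect size 1.0 and 90.7% at 1.2) and are not in question here.

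**Formula.** For an exposure that varies both within and between sites of equal size m, the true variance divided by the variance computed under independence is about

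VIF = 1 + (m − 1) × ρx × ρy,

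where ρx is the ICC of exposure and ρy the ICC of the outcome. The standard error is understated by √VIF, and the real two-sided type I error of a nominal 5% test is 2 × [1 − Φ(1.96/√VIF)].

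**STRIDE inputs.**
- From the plan: 95,000 Veterans; at least 32 enrolled sites; SD of site penetration 9%.
- Assumed: mean penetration p = 20%; 16 to 32 adopting sites; ρy from 0.01 to 0.05; equal site sizes.

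m = 95,000/32 = 2,969.
ρx = SD²/[p(1 − p)] = 0.0081/0.16 = 0.0506.
- ρy = 0.01: VIF = 1 + 2,968 × 0.0506 × 0.01 = 2.50; √VIF = 1.58; type I error 22%.
- ρy = 0.05: VIF = 1 + 2,968 × 0.0506 × 0.05 = 8.51; √VIF = 2.92; type I error 50%.

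SE factor and real type I error in several settings:

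| Setting | ρy 0.01 | ρy 0.02 | ρy 0.05 |
|---|---|---|---|
| 32 sites, mean 20%, SD 9% | 1.58; 22% | 2.00; 33% | 2.92; 50% |
| 16 sites, mean 20%, SD 9% | 2.00; 33% | 2.65; 46% | 4.00; 62% |
| 32 sites, mean 10%, SD 9% | 1.92; 31% | 2.52; 44% | 3.79; 60% |
| 32 sites, mean 20%, SD 5% | 1.21; 11% | 1.39; 16% | 1.82; 28% |

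The last row (ρx = 0.0025/0.16 = 0.0156) allows for adopting sites being more alike than all enrolled sites. At ρy = 0.005 the first row would give 1.32 and 14%.

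A null simulation of the plain treated-minus-untreated difference (32 sites, mean 20%, SD 9%) gave 20%, 29% and 48% at the three ICCs, close to the formula.

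**Confounding.** The table needs no correlation between site uptake and site outcome. When a correlation of −0.3 to −0.5 was assumed in a null simulation with weights that omit site, a spurious effect of about 0.01 to 0.06 outcome SD appeared, and rejection rates were about 31% to 98%. With site in the propensity model, bias was about zero and rejection 4% to 6%, for 16 or 32 sites.

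**Caregivers FIRST.** From the plan: about 20,000 Veterans and over 100 sites expected to implement. Assumed: 100 to 150 sites, ρx from 0.02 to 0.10, ρy from 0.01 to 0.05. With 100 sites m = 20,000/100 = 200.
- Upper end (100 sites): VIF = 1 + 199 × 0.10 × 0.05 = 2.0; SE factor 1.41; type I error 17%.
- Lower end (150 sites, m = 133): VIF = 1 + 132 × 0.02 × 0.01 = 1.03; SE factor 1.01; type I error 5%.

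**The case against.** The strongest reply is that the plan is silent, not wrong. The covariates are still to be chosen as key determinants of participation. If participation really runs from 0% to 40% by site, site meets that rule, and the simulation shows that site in the propensity model removes most of the problem. The analyses are exploratory, in projects whose primary goal is to compare implementation strategies.

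Much of this stands, and it rules out several stronger readings that a reader might infer:

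- *That the plan has decided to exclude site or to treat Veterans as independent.* Nothing says so. Independence is what results if the stated method is run with nothing added.
- *That the STRIDE patient-level model is a weighted generalized linear model.* That is named only for Caregivers FIRST. In the STRIDE text, generalized linear models are for implementation outcomes by arm.
- *That site confounding is certain.* It depends on a correlation between site uptake and site outcome. The choice of stratifiers makes one plausible, but the plan gives neither its size nor its direction.
- *That both programs are hit equally, or by the full cluster design effect.* For STRIDE at 32 sites that effect would be 15.8 to 149 for ICCs of 0.005 to 0.05. It does not apply, because exposure varies within sites. For Caregivers FIRST the inflation may be near nil.
- *That these analyses are the only evidence of patient benefit.* Group PT records function, pain and satisfaction, and the background cites earlier trials of Group PT and Caregivers FIRST and a STRIDE demonstration.

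It is also fair that the 0% to 40% range includes sites with no activity, whereas the weighted sample comes from adopters, so the 9% SD may be too large here.

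What does not fall away is the omission. Even if site enters as a covariate, the variance stays unspecified. The simulation had no true effect; if the effect differs between sites, weighting by site does not make an independence-based interval valid. Conversely, a clustered variance alone does not remove site confounding. Both need stating.

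**Conclusion.** The point holds as a gap in the method of two exploratory analyses, and filling it could change the results materially for STRIDE. If site is ignored there, the standard error is understated about 1.6- to 2.9-fold and a nominal 5% test rejects a true null about 20% to 50% of the time. This assumes 32 adopting sites of equal size, mean penetration of 20%, the plan's SD of 9% and outcome ICCs of 0.01 to 0.05. An SD of 5% among adopters brings the range down to about 11% to 28%; fewer adopting sites raise it. Residual site confounding would come on top if uptake and outcome are correlated across sites. For Caregivers FIRST, with about 200 Veterans per site, type I error is about 5% to 17%, again on assumed inputs. The formula describes an unweighted contrast, so these are orders of magnitude and not predictions for the final weighted model. The randomized site-level comparisons in both projects are untouched.

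**What to change.** Amend the Analyses text of Implementation Projects 2 and 3 and both restatements under Data Analysis and Statistical Considerations, before any patient-level outcome is analyzed:

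1. **Weights.** Include site in the propensity model as site effects, or weight within site where counts allow. Adoption of STRIDE requires only five patients with a walk, so low-uptake sites can produce extreme weights. State in advance the weight checks and how such sites will be handled.
2. **Variance.** Compute confidence intervals with robust variance clustered on site and a small-sample correction, or with a bootstrap that resamples whole sites. The correction matters most for STRIDE, where few sites may adopt. Either method also covers repeat stays at the same site, should the STRIDE data contain them.
3. **Model.** Name the STRIDE patient-level outcome model, as is done for Caregivers FIRST.

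No new data are needed. The cost is a few sentences, some weight diagnostics and slightly wider intervals. If the team already intends this, only the sentences are needed.
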